7.3. Lost to Follow Up

A participant will be considered lost to follow-up if he or she repeatedly fails to return for scheduled visits and is unable to be contacted by the study site.

The following actions must be taken if a participant fails to return to the clinic for a required study visit:

- The site must attempt to contact the participant and reschedule the missed visit as soon as possible and counsel the participant on the importance of maintaining the assigned visit schedule and ascertain whether or not the participant wishes to and/or should continue in the study.
- Before a participant is deemed lost to follow up, the investigator or designee must make every effort to regain contact with the participant (where possible, 3 telephone calls and, if necessary, a certified letter to the participant's last known mailing address or local equivalent methods). These contact attempts should be documented in the participant's medical record.
- Should the participant continue to be unreachable, he/she will be considered to have withdrawn from the study.

8. STUDY ASSESSMENTS AND PROCEDURES

- Study procedures and their timing are summarized in the SoA.
- Protocol waivers or exemptions are not allowed
- Immediate safety concerns should be discussed with the sponsor immediately upon occurrence or awareness to determine if the participant should continue or discontinue study treatment.
- Adherence to the study design requirements, including those specified in the SoA, is essential and required for study conduct.
- All screening evaluations must be completed and reviewed to confirm that potential participants meet all eligibility criteria. The investigator will maintain a screening log to record details of all participants screened and to confirm eligibility or record reasons for screening failure, as applicable.
- Procedures conducted as part of the participant's routine clinical management (e.g., blood count) and obtained before signing of ICF may be utilized for screening or baseline purposes provided the procedure met the protocol-specified criteria and was performed within the time frame defined in the SoA.
- The maximum amount of blood collected from each participant over the duration of the study will not exceed 367.4 mL for male participants and 371.4 mL for female participants.
- Repeat or unscheduled samples may be taken for safety reasons or for technical issues with the samples.

8.1. Efficacy Assessments

No efficacy assessment will be conducted in this Bioequivalence study.

8.2. Safety Assessments

Planned time points for all safety assessments are provided in the SoA.

The participants will be monitored for occurrence of adverse events and serious adverse events throughout the study. Safety evaluation will be done on the basis of outcomes of physical examination, vital signs measurement and clinical laboratory results. The activities will be performed during each study period and during post study evaluation as given in the SoA.

Additionally, any other assessment including laboratory test(s) will be done if judged necessary by the Principal Investigator (PI) or authorized trained personnel at any time during the course of study.

Post study evaluation will be done at the time of collection of last PK sample in last study period. Physical examination and measurement of vital signs (blood pressure, pulse rate, respiration rate and body temperature) performed at the time of check-out will be considered for post-study evaluation if the timing of post study evaluation and check-out coincides.

If any participant fails to complete the study or is discontinued from the study, the post-study evaluation will be done either on the day of discontinuation or before/at the end of study. If the post study evaluation is not completed within this time frame due to any reason, the same can be attempted at later stage at the discretion of Principal Investigator.

The reason for not completing the study will be specified in the respective CRF and the clinical report.

The participants may also report spontaneously any inconvenience or AEs to the monitoring staff at any time during the study or after check-out within the total number of days not exceeding the washout period.

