- e. For all participants, ALT will be done before check-in for each study period. For female participants, serum pregnancy test (Serum (β) Beta- hCG) will be done before check-in for each study period.
- f. Single oral dose of the either of two test product or reference product will be administered as per randomization with 240 ± 2 mL of water at ambient temperature under fed condition.
- g. Total number of blood samples (5 mL per sample): 22 per period.
Sampling times: Pre-dose (collected within 01.00 hour prior to dosing) and at 00.50, 01.00, 01.50, 02.00, 02.50, 03.00, 03.50, 04.00, 04.50, 05.00, 05.50, 06.00, 06.50, 07.00, 08.00, 10.00, 12.00, 24.00, 48.00, 72.00 and 96.00 hours post dose. The detailed description on blood sample collection is provided in section 8.5 Pharmacokinetics.
Blood samples will be collected in Na-Heparin Vacutainer.

Blood samples after 24.00 hours will be collected on ambulatory basis.
- h. Urine examination for drugs of abuse test will be done on check-in Day for each study period.
- i. Physical examination, measurement of blood pressure, pulse rate, respiration rate and body temperature, serum pregnancy test (Serum (β) Beta- hCG) (for female participants), Haematology, biochemistry and urinalysis will done at post study or on early discontinuation of participant.

2019N413557_00

CONFIDENTIAL

2019N423206_00
212504

√ indicates the occurrence, * indicates day starts from post-dose.

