Following a washout of at least 7 days (not more than 14 days), participants will be crossed over in Period 3 to receive the treatment according to the assigned sequence. They will be admitted into the clinical facility to complete physical examination and confirm eligibility again on Day 14. Eligible participants will take Test Product (T1): 1 x 500 mg Tablet or Test Product (T2): 1 x 250 mg Tablet or Reference Product (R): 1 x 500 mg Tablet once on Day 15 and blood samples will be collected at a set of time points (refer to SoA) pre and post dosing from Day 15 to Day 19. Post study evaluation will be done at the time of collection of last PK sample in last study period.

The analyst from bioanalytical facility will be blinded to the sequence of administration of Test and Reference product to the individual participant.

Safety data collection includes physical examinations, laboratory tests, vital signs measurements and recording of adverse events. Other clinical assessments will also be performed as appropriate. Planned time points for all safety assessments are provided in the SoA.

Participants will complete follow-up 5 days after last dosing, and complete monitoring of any adverse events.

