7.2. Participant Discontinuation/Withdrawal from the Study

- A participant may withdraw from the study at any time at his/her own request or may be withdrawn at any time at the discretion of the investigator for safety, behavioral, compliance or administrative reasons. This is expected to be uncommon.
- If participant is found positive for breath alcohol test in any ambulatory visit, then the ambulatory sample of that particular visit will not be collected. However, he/she may be requested to come for subsequent ambulatory samples in same study period, if continuation in the study is not expected to have any significant impact on the safety or PK outcome in the judgement of Investigator.
- The decision to withdraw the subject if suffering from vomiting/diarrhoea (3 or more consecutive watery stools) at or before two times of median T_{max} (8 hours) will be taken by the Investigator considering the nature and amount of vomitus, likely/anticipated impact on the study outcome and the participants' health status.
- If participant is dropped out due to personal reasons in a given period, he can be continued in subsequent periods if the PK data generated through such participation can be used for statistical analysis.
- At the time of discontinuing from the study, if possible, an early discontinuation visit should be conducted, as shown in the SoA. See SoA for data to be collected at the time of study discontinuation and follow-up and for any further evaluations that need to be completed.
- The participant will be permanently discontinued both from the study treatment and from the study at that time.
- If the participant withdraws consent for disclosure of future information, the sponsor may retain and continue to use any data collected before such a withdrawal of consent.
- If a participant withdraws from the study, he/she may request destruction of any samples taken and not tested, and the investigator must document this in the site study records.

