8.3.1. Time Period and Frequency for Collecting AE and SAE Information

- All SAEs will be collected from the start of treatment until the follow-up visit at the time points specified in the SoA (Section 1.3).
- Medical occurrences after obtaining informed consent but before the initiation of study treatment will be recorded on the Medical History/Current Medical Conditions section of the case report form (CRF) not the AE section.
- All SAEs will be recorded and reported to the sponsor or designee immediately and under no circumstance should this exceed 24 hours of occurrence of SAE, as indicated in [Appendix 3](#). The investigator will submit any follow up information to the sponsor within 24 hours of occurrence.
- Investigators are not obligated to actively seek AEs or SAEs after the conclusion of the study participation. However, if the investigator learns of any SAE, including a death, at any time after a participant has been discharged from the study, and he/she considers the event to be reasonably related to the study treatment or study participation, the investigator must promptly notify the sponsor.

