10.2. Appendix 2: Clinical Laboratory Tests

- The tests detailed in [Table 1](#) will be performed by the local laboratory of CRO.
- Protocol-specific requirements for inclusion or exclusion of participants are detailed in [Section 5](#) of the protocol.
- Additional tests may be performed at any time during the study as determined necessary by the investigator or required by local regulations.
- Pregnancy Testing Refer to [Section 5.1](#) Inclusion Criteria for screening pregnancy criteria.
- Pregnancy testing serum (Serum (β) Beta- hCG) should be conducted before check-in for each study period during treatment
- Pregnancy testing serum should be conducted at the end of relevant systemic exposure.
- Additional serum pregnancy tests may be performed, as determined necessary by the investigator or required by local regulation, to establish the absence of pregnancy at any time during the participant's participation in the study.

Table 1 Protocol-Required Safety Laboratory Assessments

Test Description	Reference range	Clinically Acceptable Limit
HEMATOLOGY		
Haemoglobin	12.5 - 18.0 g/dL - Male 11.5 - 16.0 g/dL - Female [#]	12.3 - 18.0 g/dL - Male 11.0 - 16.0 g/dL - Female [#]
Erythrocyte Count	4.5 - 5.9 million/cmm - Male 4.0 - 5.1 million/cmm - Female [#]	4.0 - 7.1 million/cmm - Male 3.6 - 5.6 million/cmm - Female [#]
PCV (Packed Cell Volume)	41.5 - 50.4% - Male 35.9 - 44.6% - Female [#]	To be correlated with hemoglobin value
MCV (Mean Corpuscular Volume)	80 - 96 μm ³	
MCH (Mean Corpuscular Haemoglobin)	27.5 - 33.2 pg	
MCHC (Mean Corpuscular Haemoglobin-Concentration)	33.4 - 35.5g/dL	
WBC Count	4400 - 11000 /cmm	3960-12100 /cmm

(Contd...)

Test Description	Reference range	Clinically Acceptable Limit
Differential Count		
Neutrophils	40 - 80 %	36 - 88 %
Eosinophils	0 - 7 %	upto 14 %
Test Description	Reference range	Clinically Acceptable Limit
Basophils	0 - 2 %	0 - 2 %
Lymphocytes	20 - 40 %	18 - 44 %
Monocytes	2 - 10 %	2 - 10 %
Platelet Count	150 - 450 x 1000/cmm	135 - 495 x 1000/cmm
BIOCHEMISTRY		
Blood urea	Upto 50 mg/dL	Upto 55 mg/dL
Blood Glucose (Random)	70 to 130 mg/dL	63 to 140 mg/dL
Blood Urea Nitrogen	Upto 23.3 mg/dL	Upto 25.0 mg/dL
Serum Creatinine	0.7 - 1.2 mg/dL - Male	0.6 - 1.3 mg/dL - Male
	0.5 - 0.9 mg/dL - Female [#]	0.4 - 1.0 mg/dL - Female [#]
Serum Bilirubin – Total	0.0 to 1.0 mg/dL	0.0 - 1.47 mg/dL
Serum Bilirubin – Direct	0.0 to 0.2 mg/dL	0.0 - 0.3 mg/dL

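### The early-discontinuation rule lets the only post-study evaluation fall before the protocol's own 5-day adverse-event follow-up and end-of-exposure pregnancy test

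*Protocol*

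**What the plan says.** Two general statements set the standard. Protocol Section 4.1: "Participants will complete follow-up 5 days after last dosing, and complete monitoring of any adverse events". Appendix 2 (Section 10.2): "Pregnancy testing serum should be conducted at the end of relevant systemic exposure". Neither exempts participants who leave early.

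The rules a site would apply to an early leaver are these:

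- **Section 8.2:** "the post-study evaluation will be done either on the day of discontinuation or before/at the end of study". No minimum time after the last dose is given. A later attempt, at the investigator's discretion, is mentioned only for an evaluation that was not completed.
- **Schedule of Activities (SoA), Section 1.3:** one column serves both the Day 19 post-study visit and early discontinuation. Footnote i puts the examination, vital signs, serum hCG and laboratory tests there: "Haematology, biochemistry and urinalysis will done at post study or on early discontinuation of participant".
- **Section 7.2:** the discontinuation visit takes place, if possible, when the participant leaves, and then "The participant will be permanently discontinued both from the study treatment and from the study at that time".
- **Section 8.3.1:** "All SAEs will be collected from the start of treatment until the follow-up visit", at the SoA time points. The investigator has no duty to look actively for events once participation has ended.

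Withdrawal soon after a dose is foreseen. Section 7.2 has a provision beginning "The decision to withdraw the subject if suffering from vomiting/diarrhoea (3 or more consecutive watery stools) at or before two times of median" Tmax, which it gives as 8 hours.

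**The concern.** Safety and tolerability is the secondary objective. For ordinary single doses the protocol treats the 5 days after the last dose as a period that needs attention: Section 5.3.3 advises avoiding strong sunlight until then, and Section 8.2.4 has clinically significant laboratory values in that window repeated. Completers are seen at 96 h. Someone who leaves at 8 or 24 h may have the whole post-study evaluation that day, and no later contact or test is itemised for that person. A new adverse event in the remaining days would come to light only if the participant reported it, and the pregnancy test might be done while drug is still circulating.

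**Working it through.** The question is mainly one of text. The plan states no figure of its own to reproduce, so the arithmetic below only sizes the gap.

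**1. Follow-up point in completers.** The last dose is on Day 15 and the post-study evaluation on Day 19, with the last PK sample: 4 × 24 h = 96 h. Counting the dosing day as Day 1, this is Day 5, which is how the 5-day follow-up in Section 4.1 is met.

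**2. Shortfall for a same-day evaluation at time t after the last dose:** max(0, 96 − t).

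| t (h) | Shortfall (h) |
|---|---|
| 8 | 88 |
| 24 | 72 |
| 48 | 48 |
| 72 | 24 |
| 96 | 0 |
| 144 (Day 1 to Day 7, or Day 8 to Day 14) | 0 |

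These are hours of missing follow-up, not a probability of missing an event.

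**3. Is exposure over at that time?** Section 2.2 gives a terminal half-life h of 9.5 to 21 h. Assuming simple first-order decline, the fraction remaining is 0.5^(t/h).

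| t (h) | h = 21 h | h = 9.5 h |
|---|---|---|
| 24 | 45% | 17% |
| 48 | 21% | 3% |
| 72 | 9% | 0.5% |
| 96 | 4% | 0.1% |

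96 h is 96/21 = 4.6 to 96/9.5 = 10.1 half-lives, in line with the protocol's statement of more than 3. Section 2.2 also describes prolonged absorption, with peak levels held for 10 to 20 h. The simple formula would therefore tend to understate what is left early on. An hCG on the day of an early withdrawal can fall before exposure has ended. Appendix 2 gives no hour for the end of exposure. I take 96 h because completers have their post-study test then.

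**4. Who is outside the gap.**

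- Participants who miss one period for personal reasons but return: "he can be continued in subsequent periods if the PK data generated through such participation can be used for statistical analysis".
- Participants withdrawn at a Day 7 or Day 14 check-in, when 96 h has already passed.
- Participants whose site chooses the later option in Section 8.2 and evaluates them at 96 h or after.

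**5. What still operates after a same-day evaluation.** Section 8.3 keeps the investigator responsible for AEs that are serious, related or led to discontinuation. Section 8.3.3 requires proactive follow-up after an initial report. Section 8.2.4 repeats clinically significant laboratory values. Section 8.2 accepts spontaneous reports after check-out for up to the washout length. Section 8.3.5 collects pregnancy details for 6 months. Each acts on something already detected or reported. What is left is the new, unreported event.

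**6. How many participants?** The plan randomises at most 36 and expects approximately 27 evaluable; 36 − 27 = 9 is a planning allowance for all losses. It is not an upper limit on withdrawals, and neither document says when withdrawals would occur. No count can be derived.

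**The case against.** The best defence is that the general rules already cover these participants. Section 4.1 and Appendix 2 have no exception for withdrawals, and Section 8.2 offers a later evaluation as an alternative, so a site can satisfy all three. Section 7.2 also points to the SoA for follow-up and any further evaluations, and the 5-day laboratory window in Section 8.2.4 is worded so that it can run past participation. All of this stands. Same-day evaluation is permitted, not required, and a reader who infers that the plan provides nothing after withdrawal goes further than the text.

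Three other strong readings are tempting and also fail:

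- **That SAE collection stops at the same-day evaluation.** Section 8.3.1 runs collection to the follow-up visit, and nothing says the same-day evaluation is that visit.
- **That participants withdrawn for vomiting or diarrhoea go unmonitored.** The event that led to withdrawal is followed under Section 8.3.
- **That pregnancies would be missed.** The documents do not show that a later test would find more. A negative test is needed within 1 day before each dose, and contraception continues for at least 1 month after the last. The hCG point is one of consistency with Appendix 2.

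The SoA's silence should also be read with care. In the text available, the AE arrows for Period 3 are not legible, and the early-discontinuation column carries a mark with no matching footnote. The point does not depend on either, because Sections 8.2, 7.2 and 8.3.1 carry it.

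The defence does not remove the conflict. The general statements are not carried into the operative rule, and Section 8 tells sites that timing follows the SoA. A site could do exactly what Section 8.2 allows and still miss the Section 4.1 follow-up point.

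**Conclusion.** The protocol is inconsistent for participants withdrawn less than 96 h after a dose. Section 4.1 and Appendix 2 set a follow-up standard that the early-discontinuation rule does not enforce. The shortfall is up to 88 h for an evaluation at 8 h and zero from 96 h on. It affects only new events that the participant does not report, and the timing of one pregnancy test. Impact is low: it bears on participant safety and descriptive safety data, and leaves the bioequivalence and dose-proportionality conclusions untouched. The conclusion assumes that a site uses the same-day option and treats participation as over, and it takes 96 h as the working end of follow-up and exposure. It is an improvement to consider, at trivial cost.

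**What to change.** Keep the day-of-discontinuation evaluation, because it secures at least one post-dose panel while the participant is present. In Section 8.2 and SoA footnote i, with matching words in Sections 7.2 and 8.3.1, add that when this evaluation falls less than 96 h after the last dose, and unless consent is withdrawn:

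- AE and SAE collection continues to at least 96 h (Day 5) after that dose, with one active enquiry by telephone or visit;
- women of childbearing potential have the Appendix 2 end-of-exposure serum hCG at or after that point;
- other laboratory tests are repeated only if clinically indicated.

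If 96 h has already passed, nothing more is needed. The SoA copy in SAP Appendix 1 should be updated to match. No analysis changes, since SAP Section 10.5.1 already lists and summarises available data from withdrawn participants.

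The cost is one short contact for a few participants, plus a 2 mL sample for women of childbearing potential (Section 8.5 budgets hCG at 2 mL each). That is less than one undrawn 5 mL PK sample, and Section 8 allows unscheduled safety samples. Some participants may decline, and this should be recorded.

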8.2.1. Physical Examinations

- A complete physical examination will include, at a minimum, assessments of the Cardiovascular, Respiratory, Gastrointestinal and Neurological systems. Height and weight will also be measured and recorded.
- Demographic information will include participant registration number, initials, date of birth, race, age, gender, height, weight and Body Mass Index (BMI) of the participants.
- Investigators should pay special attention to clinical signs related to previous serious illnesses.

8.2.2. Vital Signs

- Blood pressure, pulse rate, respiration rate and body temperature will be assessed as outlined in the SoA (see Section 1.3).

8.2.3. Electrocardiograms

- 12-lead ECG will be obtained as outlined in the SoA (see Section 1.3).

8.2.4. Clinical Safety Laboratory Assessments

- Refer to [Appendix 2](#) for the list of clinical laboratory tests to be performed and to the SoA for the timing and frequency.
- The investigator must review the laboratory report, document this review, and record any clinically relevant changes occurring during the study in the AE section of the CRF. The laboratory reports must be filed with the source documents. Clinically significant abnormal laboratory findings are those which are not associated with the underlying disease, unless judged by the investigator to be more severe than expected for the participant's condition.
- All laboratory tests with values considered clinically significantly abnormal during participation in the study or within 5 days after the last dose of study treatment should be repeated until the values return to normal or baseline or are no longer considered significantly abnormal by the investigator or medical monitor.
- If such values do not return to normal/baseline within a period of time judged reasonable by the investigator, the etiology should be identified and the sponsor notified.
- All protocol-required laboratory assessments, as defined in [Appendix 2](#), must be conducted in accordance with the laboratory manual and the SoA.

8.2.5. Suicidal Ideation and Behaviour Risk Monitoring

Not Applicable.

8.3. Adverse Events and Serious Adverse Events

The definitions of an AE or SAE can be found in [Appendix 3](#).

AEs will be reported by the participant (or, when appropriate, by a caregiver, surrogate, or the participant's legally authorized representative).

The investigator and any qualified designees are responsible for detecting, documenting, and reporting events that meet the definition of an AE or SAE and remain responsible for following up AEs that are serious, considered related to the study treatment or the study, or that caused the participant to discontinue the study (see Section 7).

